*Intervention group:* Intervention group participants will monitor and report step count data daily for six weeks, after which they will complete a telephone follow-up survey. For the first two-week period, a random half of the intervention group participants will receive IVR calls and half SMS messages; for the second two weeks these groups will ‘switch’; and all intervention group participants will be asked to use the automatic sync feature for the final two weeks of the six-week period.

The commercially-available Fitbit Zip™ pedometer and activity tracker can be attached to the participant’s waistband, belt, shirt, or stowed in his/her pocket. The Fitbit wirelessly syncs data from the tracker to the Fitbit software, or through an app compatible with most smartphones. The software is free for download on both Macs and PCs. Study staff will provide the activity tracker at an orientation session and assist with downloading the software including creation of a study-specific user name for downloading step count data. The participant will be asked to not add identifiable information to the Fitbit site during the course of the study.

Participants will be instructed to wear their pedometer during waking hours, except showering, bathing, or swimming, every day throughout their enrollment in the study. At any time if the participant has questions regarding the use of the pedometer or problems uploading step counts, a study staff member can be contacted by phone to assist. Study staff will retrieve users’ step

count data in three different ways, using each mode for a 2-week period (for a total of 6 weeks wearing the Fitbit and reporting data) as described below:

- *Manual upload:* Participants will be asked to use the display on their FitBit to view and then manually input daily step counts via daily IVR calls they will receive at evening times convenient to them. If the initial IVR call is missed, the system will try again 15 minutes and one hour later. For the SMS mode, participants will designate the time of evening they would like to receive their daily text. A second text will be sent one hour later if there is no response to the first.

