- *Automatic upload:* As described above, the research assistant will instruct participants in how to set up the FitBit so that data *automatically uploads* to the intervention website. Note that during this set-up process, the devices will be paired with a study account, and the email address provided will belong to the study. The information provided to the Fitbit company during set-up will not be identifying. It will include a study username, a masked birthdate (01/01/birth year plus or minus a constant), and a height and weight that is the male or female average, as appropriate.

*Control group:* Control group members will not track their steps during the study period, but will participate in baseline and follow-up data collection, after which they will receive a FitBit to keep.

Data collection:

Data will be collected via telephone by a trained research assistant at baseline and following the 6-week intervention.

Measures:

*Primary outcomes:*

Adherence to reporting will be indicated by the proportion of days with successfully logged step-counts, i.e., reported days/14 total days for each of the three reporting modes.

Pain interference: 4-item subscale from the PROMIS-29 Adult Profile, measured at baseline and follow-up.

*Secondary outcomes:*

Physical functioning: 4-item subscale from the PROMIS-29 Adult Profile, measured at baseline and follow-up.

Social participation: 4-item subscale from the PROMIS-29 Adult Profile, measured at baseline and follow-up.

Validity of manually-reported step counts will be assessed by comparing up to one month of IVR or SMS- collected data to data collected by syncing the device. Validity of the data will also be

assessed by examining associations between step data and relevant baseline characteristics (e.g., functioning scores, comorbidities, and age).

*Other baseline survey measures* (to characterize sample and/or as potential moderators of adherence and outcomes): *Demographics and health*: age, gender, education, race/ ethnicity, marital status, health literacy, comorbidities, cognitive functioning, physical activity. *Pain-related*: pain duration, number and location of pain sites, pain treatments, pain centralization. *Technology-related*: attitudes toward technology, eHealth literacy, social support for technology use.

*Staff burden*: Number of participant calls to the study technical support line, time spent giving technical assistance, and difficulties encountered as described in staff notes.

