#### Statistical Analysis Plan

Descriptive statistics will be calculated for baseline variables, comparing intervention and control groups using independent-sample t tests for continuous variables and chi-square tests for categorical variables, and on survey items related to satisfaction, acceptability, and adherence to step count reporting.

*Step data collection adherence:* (Days provided/14 days anticipated) among the three intervention modes, within and across subjects;

*Validity of manual step reports:* Proportion of days/21 days that manually-collected (SMS and IVR) and FitBit-stored counts are within 50 steps of each other will be calculated.

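### The only agreement statistic for manual step reports, the share of days within 50 steps, shows neither the direction nor the size of disagreement, and its device comparator is not defined

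*Combined protocol and SAP*

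**What the plan says.** Aim 2b (B. Specific Aims) is to judge manual step reports against what the device stored. The Statistical Analysis Plan gives this one agreement measure: the proportion of days, over 21, on which the manual and "FitBit-stored counts are within 50 steps of each other".

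The comparator is described in three places, never with a clock time. Aim 2b and the SAP refer to counts stored on the device. The secondary outcomes in C. Methods compare the manually collected "data to data collected by syncing the device".

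Timing is set out in C. Methods, under the intervention group:
- For IVR, participants "manually input daily step counts via daily IVR calls they will receive at evening times convenient to them". Unanswered calls are repeated twice, after a quarter of an hour and after an hour.
- For SMS, each person likewise picks an evening hour, and silence prompts one reminder: "A second text will be sent one hour later if there is no response to the first".
- Wear is meant to cover the whole waking day, apart from bathing and swimming: "Participants will be instructed to wear their pedometer during waking hours".

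The secondary outcomes add a second kind of validity evidence, "assessed by examining associations between step data and relevant baseline characteristics". That is useful, but it does not measure whether a report matches the device. No signed difference, limits of agreement or similar measure is planned.

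**The concern.** Two things are lost in a single within-50 percentage.

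First, a threshold on the absolute difference discards sign and magnitude, whatever the comparator. A report that is 60 steps low and one that is 2,000 steps high count the same.

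Second, the device can go on counting after the evening report. If the stored count is the full-day total, an accurate report followed by more than 50 steps is scored as disagreement. A low percentage could then reflect misreading or mis-entry, later walking, or both.

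The study exists to inform the design of a later trial. That trial's designers would want to know whether manual reports fall short of the daily total, by how much, and whether IVR and SMS differ. The planned percentage answers none of these beyond a pass rate.

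**Working it through.** The plan states no expected agreement, so there is no figure of its own to reproduce. From the documents: tolerance 50 steps, 30 intervention participants, a 21-day denominator. Everything about later steps and error patterns below is assumed.

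**1. Direction and size.** Let d = stored minus reported. Three assumed patterns each give 70% of days within 50 steps, with exact reports on the other days:

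| Pattern on 30% of days | Within 50 | Mean d | 2.5th to 97.5th percentile |
|---|---|---|---|
| 60 steps too low | 70% | 0.3 × 60 = +18 | 0 to +60 |
| 2,000 steps too low | 70% | 0.3 × 2,000 = +600 | 0 to +2,000 |
| 2,000 too low or too high, equally often | 70% | 0 | −2,000 to +2,000 |

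The planned statistic cannot tell these apart. A signed summary can.

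**2. Later steps, full-day comparator, error-free reader.** With mean m later steps, agreement is 1 − exp(−50/m) if they are exponential, and 1 − (1 + 100/m)exp(−100/m) if gamma with shape 2:

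| m | Exponential | Gamma, shape 2 |
|---|---|---|
| 10 | 99% | >99% |
| 25 | 86% | 91% |
| 50 | 63% | 59% |
| 100 | 39% | 26% |
| 200 | 22% | 9% |

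Against the device count at report time, the same reader would score 100% throughout. The documents give no evening step data, so any row is compatible with them.

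**3. Which signed summary.** Take exponential later steps with m = 100 and no reporting error. Mean and SD are both 100, so mean ± 1.96 SD is −96 to +296. No difference can be negative here, so the lower limit is impossible. The upper limit is exceeded on exp(−2.96) = 5.2% of days. The true central 95% runs from −100 ln(0.975) = +3 to −100 ln(0.025) = +369. Percentiles describe such skewed differences correctly; normal limits do not.

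**4. Repeated days.** Suppose person means of later steps average 100 with coefficient of variation c, over 30 people × 21 days = 630 days. The total SD is 100√(1 + 2c²). The SE of the overall mean is √[(100c)²/30 + 100²(1 + c²)/630].

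| c | Total SD | SE if days were independent (SD/√630) | SE allowing for person |
|---|---|---|---|
| 0 | 100 | 4.0 | 4.0 |
| 0.5 | 122.5 | 4.9 | 10.2 |
| 1 | 173.2 | 6.9 | 19.1 |

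Clustering matters for the confidence interval of the mean. It matters little for the spread itself: in simulation at c = 0.5 the naive pooled SD was 121.5 against a true 122.5.

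**5. What the signed difference cannot do.** Rounding every report down to the hundred, with no later steps, gives a mean d of +49.5. Error-free reports with later steps averaging 49.5 give the same mean. A positive mean is consistent with later steps but not specific to them.

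**The case against.** The best reply is that the study asks for daily step counts. On a full-day comparator, steps missed after an evening report are a real shortfall of manual reporting, so scoring them as disagreement is right. This stands. A reader might infer that the within-50 proportion is contaminated or invalid. The documents do not support that: the comparator is undefined, and if the target is the daily total, the scoring is correct. What remains is that the percentage needs a label and says nothing about direction or size.

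The effect may also be negligible. Participants choose their reporting time, which could be close to bedtime, and a retry or second text moves the report later, which would tend to leave fewer steps to come. This stands too, and is why the table in the working includes a mean of 10.

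Finally, this is a secondary, descriptive outcome with no test or threshold, and signed differences could be computed later from the same counts. That is true and limits the weight of the point. It does not remove the case for planning the summary now, since the pairs are already needed for the within-50 proportion.

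**Conclusion.** The point holds as a low-cost improvement. The within-50 proportion is the only planned agreement statistic, it carries neither sign nor magnitude, and the plan does not say which device count it uses. The first two statements rest on the documents and the form of the statistic alone.

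The mixing of reporting error with later steps applies only on the full-day reading. Its size in this trial is unknown, and the 99%, 63% and 39% figures are illustrations on an assumed exponential model.

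A reader might also infer that a signed difference would separate misreporting from later walking. It would not. Only a comparison with the device count at report time could, and the documents confirm neither response time stamps nor intraday counts; the platform security section says only that responses are stored.

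The 21-day denominator is a separate matter. The two manual modes cover 2 × 14 = 28 days, and with a fixed denominator unreported days could also lower the proportion. For that reason the added summary should use only days with both counts.

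**What to change.** In the Statistical Analysis Plan, under the validity of manual reports:

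1. Keep the within-50 proportion. State the comparator (the full-day stored count, or whichever is used) and label the proportion to match. If full-day, call it agreement with the daily total, including steps after the report.
2. From days with both counts, add the signed difference (stored minus reported), separately for IVR and SMS, as mean, median and 2.5th and 97.5th percentiles (or 5th and 95th). Use percentiles rather than mean ± 1.96 SD because later steps skew the differences.
3. Give the mean a confidence interval that allows for repeated days per person, for example a bootstrap that resamples participants.
4. State that a positive difference is consistent with later steps but does not by itself separate them from under-reporting. Add a comparison with the device count at report time only if time stamps and intraday counts prove retrievable.

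Keep the planned associations with baseline characteristics. The cost is a short paragraph in the SAP and a slightly longer summary of one secondary outcome. Items 1 to 3 need no new data.

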#### *Functional outcomes*

Per the recommended scoring algorithm (see <https://www.healthmeasures.net/explore-measurement-systems/promis>), items in each PROMIS-29 subscale of Pain Interference, Physical Function, and Social Participation were summed and converted to a subscale T score, a standardized score with a population average of 50 and a standard deviation of 10. Means at baseline and follow-up of each subscale per treatment condition will be calculated.

Repeated measures analysis of variance (ANOVA) will be used to assess treatment effect: A time-by-treatment interaction term, indicating differential pre–post change by group, was the main predictor of interest.

We used chi-square tests to evaluate differences in the proportion of participants in intervention vs control groups who achieved the minimally important difference—that is, the smallest clinically relevant difference—of 3 T-score points in the PROMIS Pain Interference measure and in the proportion who increased the frequency and duration of their low-intensity walks from baseline to follow-up (vs decreased or stayed the same).

Qualitative data on satisfaction, barriers, and facilitators from open-ended survey responses will be compiled and detailed notes made from recordings of postprogram interviews and technical support logs. These were reviewed and coded, and all meaningful statements were placed by two researchers ([name]) into conceptual categories under the broad a priori themes of challenges/disadvantages and facilitators/advantages. In place of specialized software for qualitative analysis, we used standard word processing and spreadsheet apps.

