## B. Specific Aims:

1. Identify 50 adults, predominantly African American, age > 60 years with chronic musculoskeletal pain. Thirty of these participants will be randomly assigned to receive a FitBit Zip™ and instructions for reporting daily step-count data in 3 ways (2 weeks each of manual via Interactive Voice Response (IVR) telephone calls, manual via SMS (text messaging), automatic (via syncing the device with an app) (n=30); or to a control group (n=20).
2. After a six-week monitoring period: a) compare step data collection adherence (days provided/days anticipated) among the three intervention modes, within and across subjects; b) assess the validity of manual step reports by comparing them with device-stored data; and c) compare changes in functional outcomes between monitoring and control groups.

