## C. Methods

*Inclusion criteria:* Age  $\geq$  60 years, ambulatory with or without assistive device, community living; have a SMS-capable cell phone, Internet access (via smartphone, in-home or elsewhere); self-reported chronic musculoskeletal pain (pain in muscles or joints for  $\geq$  3 months);  $\geq$ 4 (1-10 scale) average pain level over last week;  $\geq$ 1 day/previous 30 when pain made it difficult to do usual activities. In addition, participants will have to be able to travel to a location in Detroit for a one-time study orientation session.

*Exclusion criteria:* serious acute illness or hospitalization in last month, planned surgery in next month or severe cognitive impairment.

*Recruitment strategies:* A total of 50 adults meeting above eligibility criteria will be recruited from the Healthier Black Elders Center Participant Resource Pool, an opt-in research registry available to UM researchers via the Pepper Center collaboration with Wayne State University. As of January 2017, the database included 1400 individuals with an arthritis diagnosis; many of these registrants are expected to meet pain-related study criteria. Secondary sources will include flyers and outreach at community locations serving Detroit seniors.

*Randomization and data collection:* After completing a baseline telephone survey, participants will be randomly allocated in a 2:1 ratio (intervention: control) using a computer-generated scheme to the monitoring condition or a no-monitoring control group. Participants in the intervention (monitoring) group will be invited to attend an orientation session in a central Detroit location where they will receive a FitBit Zip™ monitor and instructions in setting up their device and reporting data. A project hotline will be available for technical support. Participants will receive \$10 for each questionnaire completed and can keep FitBits upon study completion (control participants will receive FitBits after follow-up survey).

Participants will be asked on the follow-up survey whether they would like to be contacted in the future to learn about opportunities to participate in studies on this topic. They will be told that they will receive all current study incentives whether or not they wish to be contacted in the future, and that they can remove themselves from the “contact” list at any time.

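### The PROMIS outcomes are tested by change from baseline; adjusting for the baseline score already collected (ANCOVA) would usually be more precise and would not over-correct chance imbalance

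*Combined protocol and SAP*

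**What the plan says.** The Functional outcomes part of the SAP says "Repeated measures analysis of variance (ANOVA) will be used to assess treatment effect". The term that carries the treatment comparison is "A time-by-treatment interaction term", described as "indicating differential pre–post change by group, was the main predictor of interest".

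The C. Methods section fixes the design behind that test:

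- There are two assessments: "Data will be collected via telephone by a trained research assistant at baseline and following the 6-week intervention".
- The primary functional outcome is given as "Pain interference: 4-item subscale from the PROMIS-29 Adult Profile, measured at baseline and follow-up". Physical functioning and social participation are measured at the same two times.
- The baseline score precedes allocation: "After completing a baseline telephone survey, participants will be randomly allocated in a 2:1 ratio".

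Aim 2c in B. Specific Aims is to "compare changes in functional outcomes between monitoring and control groups", with 30 monitored and 20 control participants. Nowhere is the baseline PROMIS score entered as a covariate. The SAP only compares baseline variables between the arms, and the other baseline measures in C. Methods serve to describe the sample or as possible moderators.

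**The concern.** With one pre-randomisation and one post-treatment score, the interaction in a repeated-measures ANOVA compares mean change between arms. It subtracts the whole baseline score, as if a one-point difference at baseline carried through in full to follow-up. When the true slope is below 1, two things follow. The estimate carries avoidable noise, and any chance difference between arms at baseline is over-corrected, which pushes the estimate the other way.

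Pain interference is a primary outcome, the comparison has about 50 participants, and the results are meant to inform a later trial. At that size chance imbalance is likely and precision is scarce. The baseline score that would deal with both is already collected.

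**Working it through.** **Inputs from the documents.** Two time points; baseline before randomisation; 30 versus 20 participants (B. Specific Aims). The only SD given is 10, which is the PROMIS reference-population value, not this sample's. The plan's minimally important difference is 3 T-score points. The plan states no alpha, power, correlation or dropout, so it has no figure of its own to reproduce.

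**Assumptions.** Correlation r between baseline and follow-up from 0.3 to 0.8; SD 10 or 7 at both times, or 7 at baseline and 9 at follow-up; two-sided 5%; no dropout.

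**1. Equivalence.** On one simulated 30:20 data set with complete pairs, the interaction gave F(1,48) = 1.739, p = 0.193. The squared t for change scores was 1.739, p = 0.193. They are the same test.

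**2. Precision.** Write s0 and s1 for the baseline and follow-up SDs. The variance per participant is:

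- change score: s0² + s1² − 2·r·s0·s1
- ANCOVA: s1²(1 − r²)

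The first minus the second is (s0 − r·s1)², which is never negative, so with a common slope ANCOVA cannot lose in large samples. With s0 = s1 the ratio is (1 + r)/2. Estimating the slope at n=50 costs a factor 1 + 1/46 = 1.022.

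| SDs (baseline, follow-up) | r | Large-sample ratio | Ratio at n=50 |
|---|---|---|---|
| equal | 0.3 | 0.65 | 0.66 |
| equal | 0.5 | 0.75 | 0.77 |
| equal | 0.7 | 0.85 | 0.87 |
| equal | 0.8 | 0.90 | 0.92 |
| 7, 9 | 0.5 | 0.91 | 0.93 |
| 7, 9 | 0.6 | 0.95 | 0.97 |
| 7, 9 | 0.7 | 0.99 | 1.01 |

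For 95% CI half-widths, the SE multiplier is √(1/30 + 1/20) = 0.2887, with t on 48 df (change score) or 47 df (ANCOVA). At r = 0.5:

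- SD 10: 5.8 versus 5.1 T points
- SD 7: 4.1 versus 3.6
- SDs 7 and 9: change-score variance 49 + 81 − 63 = 67, half-width 4.8; ANCOVA variance 81 × 0.75 = 60.75, half-width 4.6

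C. Methods gives a 2:1 ratio, about 33:17 of 50. The multiplier is then 0.2985, and the variance ratios are unchanged.

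**3. Chance imbalance.** If the arms differ by d at baseline, the change-score estimate is shifted by −(1 − r·s1/s0)·d, which is −(1 − r)·d with equal SDs.

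- SD 10: d has SE 10 × 0.2887 = 2.9, median absolute size 1.9, and a 30% chance of exceeding 3 points.
- SD 7: SE 2.0, median 1.4, and a 14% chance.

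The shift from a median-sized d is:

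- r = 0.5, equal SDs: 0.7 (SD 7) to 1.0 (SD 10) T points
- r = 0.7, equal SDs: 0.4 to 0.6
- SDs 7 and 9: (1 − 0.5 × 9/7) × 1.36 = 0.49 at r = 0.5, and (1 − 0.7 × 9/7) × 1.36 = 0.14 at r = 0.7

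**4. Simulation.** With 40,000 trials per setting at 30:20 over ten SD and correlation settings, type I error was 4.8 to 5.2% for both tests. At r = 0.5 with equal SDs, the slope of estimation error on baseline difference was −0.50 for the change score and 0.00 for ANCOVA. Power for an illustrative 3-point effect at r = 0.5, change score versus ANCOVA:

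- SD 10: 17.5% versus 21.3%
- SD 7: 30.9% versus 38.5%
- SDs 7 and 9: 24.1% versus 25.4%

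**The case against.** The planned test is not wrong. It is standard, unbiased over randomisations, holds its type I error, and matches the wording of aim 2c. The study is preliminary, no stated decision depends on the width of the interval, and power for 3 points is low under either model. All of that stands, and it is why this is a suggestion and not a defect.

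The size of the gain also rests wholly on assumed SDs and correlations. Entry requires at least 4 on a 1-10 scale for "average pain level over last week", which may narrow the baseline spread relative to follow-up. With SDs 7 and 9 at r = 0.7, ANCOVA is marginally wider (half-width 3.77 versus 3.75). Over-correction is likewise conditional: it needs r·s1/s0 below 1. With SDs 7 and 9 at r = 0.8 the shift becomes a trivial under-correction of 0.03·d. With unequal allocation and slopes that differ by arm, common-slope ANCOVA can be the less precise analysis. The equivalence to a t test is exact only for participants with both scores.

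The appeal to aim 2c does not stand. Once baseline is in the model, the treatment coefficient is the same whether the outcome is follow-up score or change. The possible loss in the settings examined (about 1% of variance) is also small beside the possible gain (up to 34%).

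**Conclusion.** The point holds as a matter of efficiency and of accuracy given the imbalance that occurs, not of validity. For complete pairs, the planned interaction test is the change-score t test, and no baseline adjustment is planned. At n=50 with equal SDs, ANCOVA would cut the variance by 8 to 34% for correlations from 0.8 down to 0.3, and would remove a shift of roughly 0.4 to 1.0 T points from a median-sized baseline imbalance at correlations of 0.7 to 0.5. If baseline spread is clearly narrower than follow-up spread, the gain may be nil. These sizes depend on SDs and correlations that the documents do not give; the direction depends on the true slope being below 1 and similar in the two arms. It is worth considering because it costs almost nothing.

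**What to change.** For each PROMIS subscale, make the primary analysis a linear model of follow-up T score on treatment and baseline T score, and report the adjusted difference with its 95% CI. Keep the repeated-measures ANOVA as a sensitivity analysis. Both use only participants with a follow-up score; to include those without one, fit a mixed model that constrains the two arms to a common baseline mean.

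The cost is one model line and a sentence of SAP wording, with no new data. Functional outcomes is written partly in the past tense. If the analysis has already been run, report both models and label the ANCOVA as a later re-fit.

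### The planned ANOVA for the PROMIS outcomes pools variance across deliberately unequal arms; arm-specific variances would be a cheap, minor improvement

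*Combined protocol and SAP*

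**What the plan says.** Methods lists as a primary outcome "Pain interference: 4-item subscale from the PROMIS-29 Adult Profile, measured at baseline and follow-up". Physical functioning and social participation are secondary outcomes measured at the same two times.

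The SAP, under Functional outcomes, states "Repeated measures analysis of variance (ANOVA) will be used to assess treatment effect" and identifies the effect of interest: "A time-by-treatment interaction term, indicating differential pre–post change by group, was the main predictor of interest". It mentions no unequal-variance test, robust standard error, variance check or sensitivity analysis. It states no alpha and plans no confidence interval.

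The arms are unequal by design. The Specific Aims give the monitoring and control sizes as "automatic (via syncing the device with an app) (n=30); or to a control group (n=20", while Methods says "participants will be randomly allocated in a 2:1 ratio (intervention: control". With 50 participants, 2:1 means about 33 and 17. The two statements do not agree with each other, but both put more people in the monitoring arm.

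**The concern.** A two-time-point ANOVA estimates one variance of change across both arms. With equal arms this does little harm, because the pooled standard error still matches the true one when the spreads differ. With unequal arms the pooled variance is weighted towards the larger arm, while the true variance of the difference depends more on the smaller arm. The standard error is then too large if the larger arm varies more, and too small if the smaller arm varies more.

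At stake are the p-value for the between-arm contrast on a primary outcome, the same tests for two secondary outcomes, and any interval later derived from the same model. The estimated difference in change is not biased by this.

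**Working it through.** **Inputs from the documents.** Total 50; arms 30:20 (Specific Aims) or 2:1, about 33:17 (Methods); two measurement times; contrast is the difference in pre-post change. The only SD given is that of the T-score metric, "a standardized score with a population average of 50 and a standard deviation of 10". That describes the reference population; it is not an SD of change and is not given by arm.

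**Assumptions.** Two-sided 5% test, normally distributed change, no dropout, and a range of SD ratios between arms. The plan has no power or standard-error figure to reproduce.

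**Step 1: what the test is.** On one simulated 30:20 data set, the ANOVA interaction and the pooled t-test on change gave the same result: F = t² = 0.0412, p = 0.840, 48 degrees of freedom.

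**Step 2: standard errors.** Write n1, s1 for the monitored arm and n2, s2 for control.

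- Pooled: √{[((n1−1)s1² + (n2−1)s2²)/(n1+n2−2)] × (1/n1 + 1/n2)}
- True: √(s1²/n1 + s2²/n2)

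Example, 30:20 with s1 = 1.25 and s2 = 1:

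- Pooled variance = (29 × 1.5625 + 19 × 1)/48 = 1.340; pooled SE = √(1.340 × 0.08333) = 0.334
- True SE = √(1.5625/30 + 1/20) = 0.3195
- Ratio = 1.046

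Example, 33:17 with s1 = 1 and s2 = 1.5:

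- Pooled variance = (32 × 1 + 16 × 2.25)/48 = 1.417; pooled SE = √(1.417 × 0.08913) = 0.355
- True SE = √(1/33 + 2.25/17) = 0.403
- Ratio = 0.881

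**Step 3: false-positive rate of the pooled test, by simulation (400,000 replicates per row; a larger rerun agreed to about 0.1 point).**

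| Arms | More variable arm | SD ratio | Pooled/true SE | Type I error |
|---|---|---|---|---|
| 30:20 | monitored | 1.25 | 1.05 | 4.1% |
| 30:20 | monitored | 1.5 | 1.08 | 3.5% |
| 30:20 | control | 1.25 | 0.96 | 6.1% |
| 30:20 | control | 1.5 | 0.92 | 7.0% |
| 33:17 | monitored | 1.25 | 1.07 | 3.6% |
| 33:17 | monitored | 1.5 | 1.13 | 2.7% |
| 33:17 | control | 1.25 | 0.93 | 6.7% |
| 33:17 | control | 1.5 | 0.88 | 8.4% |

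In the same scenarios Welch's test stays at 5.0 to 5.1%. At 25:25 the SE ratio is 1.00 for every SD ratio, and the pooled test gives 5.0 to 5.1% for ratios up to 1.5, so the unequal allocation drives the problem. Dropout that keeps the 3:2 split (27:18 or 24:16) leaves the picture unchanged.

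**Step 4: power, with assumed SDs of change in T-score points and an illustrative 6-point difference.**

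- Monitored 9, control 6: pooled 74% against Welch 79% at 30:20; 70% against 78% at 33:17.
- Both 8: pooled 72.1% against Welch 71.8% at 30:20; 69.2% against 68.3% at 33:17. This is the cost of the fix when it was not needed.

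**The case against.** The strongest reply is that nothing in the documents shows the triggering condition. There is no SD of change by arm, and no statement that uptake is expected to vary. Adherence is a primary outcome, but it counts days of step reporting out of 14 in each mode; it does not measure how much people respond to monitoring. This stands, and the point can only be conditional.

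The larger effects also need a strong assumption. If the extra spread came from independent variation in individual effect, SDs of 9 and 6 would require an effect SD of √(81 − 36) = 6.7 points, more than twice the SAP's minimally important difference of 3. With a control SD of 8 and an effect SD of 3, the monitored SD is √(64 + 9) = 8.54. The pooled SE is then only 1.3% (30:20) or 2.2% (33:17) too large, and the power loss at 6 points is under 1 point. The 6-point difference is itself twice the minimally important difference. This stands too.

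A reader might infer that the planned test produces too many false positives. The documents do not support that. It needs a zero average effect together with a control arm more variable than the monitored arm. If monitoring affects nobody, randomisation gives both arms the same distribution of change and no inflation arises. Response that varies among monitored participants points the other way, to a conservative test.

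A reader might also infer that the planned standard errors are wrong as they stand, or that faulty intervals will pass to the future trial. Repeated measures ANOVA is valid under equal variances, and the SAP plans no interval.

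What survives is that the validity of the planned test rests on an unstated and unchecked assumption, which equal arms would have made nearly harmless and which can be dropped at almost no cost.

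**Conclusion.** The point holds as a minor, conditional one. The algebra and the unequal allocation are certain; the size of the error is not, because it depends on SDs of change that the documents do not give. An SD ratio of 1.25 puts the standard error about 4 to 7% off, with type I error between about 4 and 6% at 30:20 and 3.6 and 6.7% at 33:17. A ratio of 1.5 puts it about 8 to 13% off, with type I error between about 3.5 and 7% at 30:20 and 2.7 and 8.4% at 33:17. The upper ends belong to the direction that the plan gives no reason to expect. In the more plausible direction the cost is lost power, from under 1 point for modest variation in effect to about 5 to 8 points under the strong 9-against-6 assumption. These figures assume normal change scores, a two-sided 5% level and no dropout. This is a pilot with no stated alpha or power target, so no planned operating characteristic is missed.

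**What to change.** Keep the between-arm difference in pre-post change for all three PROMIS subscales, and add a sentence under Functional outcomes saying that its standard error and p-value, and any confidence interval reported, will use arm-specific variances. Welch's test on change scores is the simplest form; a regression with HC3 standard errors is an alternative. If baseline adjustment is adopted, the same sentence is still needed, because an ANCOVA with ordinary standard errors pools variance in the same way. Reporting the SD of change by arm would also show whether the assumption mattered.

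The cost is one sentence and one software option. If the variances are in fact equal, the loss is at most about 1 point of power (0.3 at 30:20 and 0.9 at 33:17 in the example above). The estimate of Welch's test on change is the same as the planned contrast. The 30:20 and 2:1 statements should be reconciled at the same time, since the sensitivity to unequal variances is greater under 2:1.
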